Models of Care in the Transition from the Secondary to the Primary Sector among the Frailest Elderly +75; a Randomized Controlled Trial

[name]

December 27th, 2018

Models of Care in the Transition from the Secondary to the Primary Sector among the Frailest Elderly +75; a Randomized Controlled Trial

In most Western countries the elderly population increases rapidly. In Denmark, the population of elderly aged 75 years or older may amount to nearly 15 % of the entire population in 2050 compared to 9 % today (2017) (1). A large part of the elderly population is at high risk of hospitalization including more admissions and increased morbidity and mortality (2,3). The number of hospital beds is declining persistently (4), calling for shorter lengths of stay (LOS) (5,6). Increasingly complex treatments now take place outside hospital. Presently, many Danish regional hospitals establish geriatric wards and other geriatric in-hospital and outpatient services to overcome these challenges. The aim of the present PhD-study is to investigate the effects of different models of transitional care among the frailest elderly patients.

Readmission

Readmitted patients occupy many beds and other hospital resources. Patients are at a risk of high mortality (7) and decline of functional ability (8,9). More than 20 % of Danish medical patients aged 65 years or older become readmitted within 30 days after discharge (10), more frequently in the frail elderly (11). The risk of readmission is particularly high within the first week after discharge, where more than 40% of readmissions happen (12,13). Many reasons and factors for readmissions have been mentioned (11,14-16) such as: former or recent admission, duration of the index hospitalization, degree of comorbidity and low functional ability (11,15). To prevent readmissions it is important to identify the reason for admission and remove it, to ensure that the correct medication is implemented and make sure that adequate social service is provided, to convey unsolved problems to the primary care, ensure continuity during transfer and finally establish sufficient and timely follow-up after discharge (11,14-17).

Identification of patients at risk

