According to the various interventions stated above, the outcomes of relevance are readmissions (8-12,15,17,22,24-26,28-44), mortality (7,8,10,12,25,27,28,30-32,38-41,44), length of stay (LOS) (12,25,28,29,32,38,41,45), direct discharge from the ED (12,29), time at home (10,25,27,34), duration of readmission (10,25,34) and physical functional status (8,25,27,28,30,31,34,40,43-45). A successful intervention may be reflected in a shorter LOS, lower risk of readmissions, longer time at home, maintained functional status and a shorter duration of readmission. We suggest that a significant and effective intervention under the best circumstances is reflected in these outcomes. Readmissions are usually considered as such, when the admission occurs within 4 hours after and before 30 days after discharge. Among the frail, in-hospital and post-discharge mortality is high, needing frequent assessment. As shown by Pedersen et al. (7), mortality differs with regard to type of dwelling. Former studies have shown a significant and remarkable reduction of LOS (reduction from median 3 days to median 2 days) and an increase from 49 % to 56 % of patients discharged directly from the ED due to the possibility of early follow up by a geriatric team (12). Functional status is of relevance, especially combined with mortality data, since a better survival of the frailest may be combined with a worsened functional status in the total group. Patient satisfaction and costs are other relevant outcome measures with regards to the triple aim principle, but will not be included in the present Ph.D. project.

Conclusion

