The patients in the control group are discharged to usual care and do not receive early follow-up visits. Usual care features municipality services and optionally a GP home visit (see Appendix 2). Eligible control patients are consecutively included by a Research Assistant. The estimated level of frailty will be assessed by the PhD-student based on a MPI-screening tool fitted to be performed using only medical record data. This fitted tool will be tested and validated prior to the inclusion of the control group. Clinicians will be blinded to the result of the MPI-screening of the control subjects to ensure that discharge is performed in accordance with usual care.

Outcomes

The primary outcome is readmission within 30 days after discharge. Secondary outcomes are:

- Mortality 30 days after discharge and 90 days after admission
- Length of stay during primary admission and total length of stay including following readmissions
- Direct discharge from the Emergency Department
- Time at home before readmission
- Duration of readmission
- Physical functional status 30 days after discharge (Functional Recovery Score)

Statistical analyses

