Data are registered in REDCap and exported to STATA version 15 for the statistical analyses. Statistical significant results are defined as a p-value of 5% or less. The two intervention groups and the control group will be compared with regard to baseline measures. If needed, statistical corrections for demographical differences and level of frailty will be made. The use of services and other contents of follow-up will be assessed and compared if possible. Baseline data collected for the entire study population before discharge are: age, gender, date of admission, co-habitation status, number of drugs, and level of frailty measured by MPI including functional status by means of Functional Recovery Score (FRS) at discharge. Follow-up data for the control group will be collected on type of planned care after discharge. Follow-up data for the entire study population will be collected on: department of discharge, date of discharge, primary diagnosis at discharge, dwelling after discharge, readmission date, and death date. For the intervention cohort additional data are collected: date of follow-up, provided services after discharge, number and date of visits (team, GP, nurse) after discharge, phone-calls to the geriatric team or GP, nutritionist consultations, FRS after 30 days, date of dispatch of discharge summary. Additional data will be collected by review of the electronic patient records.

Outcomes

A hazard ratio (HR) for readmissions will be calculated using a Cox regression model with death as a 'competing risk' factor. The HRs of readmission with 95% confidence intervals (95% CI) for interventions I and II will be compared

individually and to the control group. The interventions will be tested in subgroup analyzes based on: patients discharged directly from the ED, type of dwelling and level of frailty. Median LOS, time at home before readmission and duration of readmission will be calculated and compared using the Wilcoxon rank-sum test. The mortality hazard ratio will be calculated also using the Cox regression model. The change in functional status at discharge and 30 days after discharge will be compared in a linear regression model. Data will be analyzed in accordance with intention-to-treat and per-protocol analysis.

Sample size

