Power analysis is based on a pilot study performed from June to December 2017 using the method stated above, and earlier studies by Pedersen et al.(7,12), where patients selected by diagnoses associated with readmission were randomized to early geriatric follow-up visits or usual care. Readmissions were reduced from 23% to 12%. Data collected during the pilot study showed 13.7% readmissions in the Intervention group I compared to 8% readmissions in the Intervention group II. Based on the pilot study data, allowing a 5% drop-out rate and a 30-day mortality rate of 10%, the number of patients in each trial arm should be 758 in order to achieve a power of 90% and a level of significance of 5%. Data collected during the same pilot study showed a 90-day mortality rate of 20.6% in Intervention group I compared to 15.6 % in Intervention group II. To achieve a power of 80% and a level of significance of 5% with regards to mortality, the sample size of each arm should be 1,019, including a 5% drop-out rate.

Perspectives

This study may uncover a need for specialized and early efforts to support transfer of the frail elderly. We may find that some of the frail elderly are poorly supported by the present follow-up procedures, suggesting that comprehensive geriatric assessment and early follow-up intervention by a community nurse and a geriatric team should gain further currency in the future. This study may contribute to dimension health care services in the future. We hope to clarify the possible need for geriatric services outside university hospitals. The results are directly transferable to Danish regional hospitals and may be of importance in other Western countries.

Ethics

The study has been approved as a quality development project by the Regional Research Ethics Committee, Central Denmark Region (journal no. 197/2017), thereby no patient consent form is needed, and further referral to the committee not required. No patient will receive less than usual care, no extra treatment or examination will be applied, and no patient will be exposed to any additional risk because of the project. Participants may decline parts of or the entire intervention, including usual care, at any time. The project, which is a part of the national rate adjustment pool-project "Early post-discharge follow-up of the frail elderly – a intersectoral effort" in the Central Denmark Region, is approved by the Danish Data Protection Agency (journal no. 2012-58-006).

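### Length of stay is analysed only by medians and a rank-sum p-value, so the plan gives no estimate of hospital days saved and no confidence interval for judging whether the arms are similar

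*Combined protocol and SAP*

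**What the plan says.** The two documents carry the same text on this point.

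- **Rationale.** The introduction states: "The number of hospital beds is declining persistently (4), calling for shorter lengths of stay (LOS". Under Perspectives: "This study may contribute to dimension health care services in the future".
- **Hypotheses.** LOS is listed in all three, each worded as one approach being as good as, or similar to, another.
- **Outcomes.** The secondary outcomes include "Length of stay during primary admission and total length of stay including following readmissions" and, separately, "Direct discharge from the Emergency Department". No window is given for the total.
- **Analysis.** Under Statistical analyses, Outcomes: "Median LOS, time at home before readmission and duration of readmission will be calculated and compared using the Wilcoxon rank-sum test". Readmission gets hazard ratios with 95% confidence intervals in the same paragraph; LOS gets neither an effect estimate nor an interval. The general rule is "Statistical significant results are defined as a p-value of 5% or less".
- **Subgroups.** "The interventions will be tested in subgroup analyzes based on: patients discharged directly from the ED, type of dwelling and level of frailty". No matching LOS analysis of ward patients is described.
- **Background figures.** Under Outcome measures, an earlier trial is credited with a "reduction from median 3 days to median 2 days) and an increase from 49 % to 56 % of patients discharged directly" from the ED. Stay by setting is not given.

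**The concern.** Bed need is the number of patients times mean days per patient. Neither a median nor a rank-sum p-value supplies that mean. Nor can a p-value above 5% support a hypothesis that two approaches are similar; the reader needs to see which differences in days remain compatible with the data.

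The second issue is how the median behaves. LOS in this trial mixes short ED stays with longer ward stays. If nearly all ED stays are shorter than nearly all ward stays, the median patient is a ward patient when direct discharge is below 50% and an ED patient when it is above. Close to that point the median is governed largely by the mix. It may then exaggerate a small change in days used, or miss a real fall in ward stay.

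**Working it through.** **Inputs from the documents.** Direct ED discharge 49% and 56%, and medians of 3 and 2 days (earlier trial, Outcome measures). 758 and 1,019 per arm, and pilot 90-day mortality of 20.6% (I) and 15.6% (II) (Sample size). Two-sided 5% is assumed, since sidedness is not stated.

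**Sample sizes.** For 13.7% v 8% at 90% power, the continuity-corrected two-proportion formula gives 659; 659 x 1.15 = 757.9, i.e. 758. For 20.6% v 15.6% at 80% power it gives 970; 970 x 1.05 = 1,018.5, i.e. 1,019. Both stated figures are reproduced. Neither concerns LOS, which has no power statement.

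**Step 1: where the median falls if ED and ward stays are fully separated (assumption).**
- At 49%: (0.50 - 0.49)/0.51 = 0.02, the 2nd percentile of ward stays.
- At 56%: 0.50/0.56 = 0.89, the 89th percentile of ED stays.

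**Step 2: separated stays, simulated.** Assumed: ED stays of 0, 1 or 2 days (20%, 50%, 30%); ward stays of 3 days or more; baseline ward mean 5.5, 7 or 9 days.

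| Change between arms | Median | Mean |
|---|---|---|
| 49% to 56%, ward stays unchanged | 3 to 2 | 9-10% lower (3.34 to 3.03; 4.11 to 3.69; 5.10 to 4.57) |
| 49% to 56%, ward mean about 17% longer | 3 to 2 | 2-3% higher |
| 56% in both, ward mean 16-36% shorter | 2 to 2 | 13-31% lower |

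In the last row the rank-sum test still responds. Its power at 758 per arm is 29-32% when the ward mean is 16-22% shorter, and 70-79% when it is 27-36% shorter.

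**Step 3: overlapping stays.** Assumed log-normal: ED median 1 day, log-SD 0.5; ward median 5 days, log-SD 0.7. Setting means are 1 x exp(0.5²/2) = 1.13 and 5 x exp(0.7²/2) = 6.39.
- Mix shift only, 49% to 56%: the mean falls 0.07 x (6.39 - 1.13) = 0.37 day (3.81 to 3.44). The median falls 0.35 day (2.02 to 1.67). There is no disproportionate jump.
- Ward median 5 to 4, 56% direct discharge in both arms: the new ward mean is 4 x 1.278 = 5.11. The overall mean goes from 0.56 x 1.133 + 0.44 x 6.388 = 3.445 to 0.56 x 1.133 + 0.44 x 5.110 = 2.883, a fall of 0.562 day; 0.562 x 758 = 426 bed-days. The median moves only from 1.67 to 1.58.

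**Step 4: power in the overlapping model** (simulated, 2,000 runs per case).

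| Case | n per arm | Rank-sum | Means |
|---|---|---|---|
| Ward median 5 to 4, 56% direct discharge | 758 | 33% | 81% |
| Same | 1,019 | 42-43% | 92% |
| Ward median 5 to 4, 30% direct discharge | 758 | about 90% | about 97% |
| Mix shift 49% to 56% only | 758 | about 60% | 36-38% |

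At 30% direct discharge the median itself moves clearly, from 3.39 to 2.74 days.

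**The case against.** Medians with a rank-sum test are conventional for skewed stays. LOS is an unpowered secondary outcome, the stated aim is effects on patients rather than bed use, costs are excluded from the project, and informing service capacity is only a hope under Perspectives. Direct ED discharge and total stay are already separate outcomes, so a change of mix would be visible beside the median.

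Two stronger readings are tempting, and the documents support neither.

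- *The cited figures show a threshold artefact.* They are four numbers without stay by setting. They fit a crossing of 50%, but a full-day jump needs nearly separated ED and ward stays, and Step 3 shows that it disappears when the distributions overlap. The earlier patients were also selected by diagnosis, whereas this trial selects on frailty score and also enrols on two geriatric wards. Its direct-discharge share is not given.
- *The plan cannot detect shorter ward stays.* That describes the median above 50% direct discharge, not the planned test. The rank-sum test uses all ranks. It loses power in one setting, does well at 30% direct discharge, and beats a comparison of means for a pure mix shift.

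So the case for replacing the planned analysis fails. What the objection does not answer is that no estimate in days, and no interval, is planned for an outcome motivated by bed pressure and named in hypotheses of similarity. Reporting direct ED discharge separately does not fill that gap.

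**Conclusion.** The concern holds as a gap in estimation. Whatever the direct-discharge share, the plan yields no difference in hospital days and no confidence interval for LOS.

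The fragility of the median is conditional. It needs direct discharge near 50%, and the full-day jump also needs nearly separated stays. Under those assumptions the median can fall by a third while mean days fall by about a tenth, or even rise by 2-3%. At 56% direct discharge a fall of 0.56 day in mean stay can leave the median almost still, with rank-sum power of about 33% against 81% for means at 758 per arm. All stay distributions here are assumed; the documents give none. The matter affects a secondary outcome and leaves the primary analysis untouched.

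**What to change.** Keep the median and rank-sum test. Beside them, pre-specify the difference in mean hospital days per randomised patient, II v I, with a bootstrap 95% confidence interval, for:

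1. the index stay; and
2. total stay over a fixed 90-day window from admission.

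Report the 90-day total alongside 90-day mortality. Death shortens hospital days, and pilot mortality was higher in group I (20.6% v 15.6%), so fewer days in an arm need not mean better care. Any breakdown into ED and ward stays should be descriptive, because setting is determined after randomisation.

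The cost is a few sentences and one bootstrap. Admission, discharge, readmission and death dates are already to be collected, and the ends of readmissions can come from the records, where the planned duration-of-readmission outcome needs them anyway. Downsides: a few very long stays widen the interval, the comparison of means is the weaker test for a pure change of mix, and the 90-day total is truncated by death.
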